5.2. Exclusion Criteria

Medical Conditions

- 1. **Skin Morbidity:** other than atopic dermatitis, the presence of a significant skin morbidity that will influence the Investigator's ability to assess the severity of the disease (e.g. psoriasis, confirmed or suspected cutaneous T-cell lymphoma, autoimmune bullous disease, fixed drug reaction and Stevens Johnson Syndrome).
- 2. **Major Diseases/Conditions:** Participants with any uncontrolled medical conditions, other than Atopic Dermatitis, that in the opinion of the investigator puts the participant at unacceptable risk or will likely interfere with study assessments or data integrity. Other medical conditions should be stable at the time of screening and be expected to remain stable for the duration of the study.
- 3. **Malignancy:** solid or hematological malignancy or a history of malignancy (in the past 5 years), *except for treated/cured* basal cell or squamous cell *in situ* skin carcinomas, cervical intraepithelial neoplasia (CIN) or carcinoma *in situ* of the cervix.

4. Infection:

- An acute infection within 2 weeks of dosing on Day 1.
- history of, or currently being treated for, a clinically significant recurrent or chronic infection/s (except very minor localised infections, for example tinea pedis).
- hospitalized for treatment of infection (anti-bacterials, anti-virals, anti-fungals or anti-parasitic agents) within 30 days of dosing on Day 1.
- 5. Known **varicella, herpes zoster**, or other severe viral infection within 6 weeks of anticipated dosing on Day 1. Or history of recurrent herpes reactivation in the past 2 years.
- 6. **COVID-19 (SARS CoV-2):**
 - Has had COVID-19 infection within 4 weeks of the initial Screening visit.

- Positive test obtained at initial Screening.
- Signs and symptoms suggestive of COVID-19 (i.e. fever, cough, etc) within 14 days of initial Screening.
- Known COVID-19-positive contacts within 14 days of initial Screening, at any time during the Screening Period, or within 14 days of dosing on Day 1.
- 7. **Tuberculosis (TB):** Evidence of active or latent TB as documented by medical history, examination, and TB testing with a positive QuantiFERON test at initial Screening visit.

NOTE: In cases where the QuantiFERON test is *indeterminate*, the participant may have the test repeated once, but they will not be eligible for the study unless the second test is negative. In cases where the QuantiFERON test is positive, the participant should be followed up as per standard of care.

- 8. **Drug Allergy or hypersensitivity:** history of clinically significant multiple or severe drug allergies or severe post-treatment hypersensitivity reactions (including, but not limited to, erythema multiforme major, linear immunoglobulin A (IgA) dermatosis, toxic epidermal necrolysis, and exfoliative dermatitis).
- 9. **Sensitivity** to any of the study interventions, or components/excipients thereof, in the opinion of the Principal Investigator (or following consultation with the GSK Medical Monitor), contraindicates participation in the study.
- 10. **Hepatic**: current or chronic history of liver disease, or known hepatic or biliary abnormalities (with the exception of Gilbert's syndrome or asymptomatic gallstones).
 - a. Alanine transaminase (ALT) >2x upper limit of normal (ULN).
 - b. Bilirubin >1.5xULN (isolated bilirubin >1.5xULN is acceptable if bilirubin is fractionated and direct bilirubin <35%).
- 11. Cardiology assessment/co-morbidity defined as: corrected Q (QTc) >450 msec (480 msec for those with Bundle Branch Block). Either QTcb (Bazett) or QTcf (Fridericia), machine or manual overread, may be used. The QT correction formula used to determine exclusion and discontinuation should be the same throughout the trial. The QTc should be based on a single value (derived from the average of triplicate readings) of ECG obtained over a brief recording period.
- 12. A participant with either a **clinical abnormality or a laboratory parameter(s)** outside of the reference range (or both) that is not specifically listed in the inclusion or exclusion criteria may only be included if the Investigator, in consultation with the GSK Medical Monitor, agrees and documents that the finding is unlikely to introduce additional risk factors that will not interfere with the study procedures or interpretation.

PRIOR / CONCOMITANT THERAPY

Any patients that are receiving medication(s) detailed in this Section will *not* be eligible for randomisation into the trial.

13. **Surgery:** major surgery (as per investigator's judgement) within 3 months prior to dosing on Day 1.

- 14. **Phototherapy:** treatment with phototherapy (narrow band ultraviolet B [NBUVB], ultraviolet B [UVB], ultraviolet A1 [UVA1], psoralen + ultraviolet A [PUVA]), within 4 weeks of dosing on Day 1.
- 15. **Sun/tanning:** prolonged sun exposure or use of tanning booths (which may confound interpretation of study data) within 2 weeks before Initial Screening.
- 16. **Bleach bath:** three or more bleach baths during any week within 4 weeks of the initial Screening visit.
- 17. **Medical Devices:** treatment of AtD with a medical device (eg, Atopiclair, MimyX, Epicerum, Cerave, etc) within 1 week of the initial Screening visit.
- 18. **Vaccines**: participant has received a live, attenuated or recombinant vaccine within 8 weeks of anticipated dosing (Day 1), or will require vaccination within 24 weeks following dosing. Note that, the recombinant adenovirus vector vaccines against COVID-19 (both human and non-human primate in type) are permitted (refer to the study reference manual, SRM).
- 19. **Systemic corticosteroids**: treatment within 30 days of dosing on Day 1. Note that, intra-articular steroids are permitted.
- 20. **Topical corticosteroids:** treatment within 7 days of dosing on Day 1.
- 21. **Biologic agents:** treatment with biologic agents (investigational and marketed monoclonal antibodies) within 12 weeks or 5 pharmacokinetic half-lives (whichever is longer) prior dosing on Day 1.
- 22. **JAK inhibitors:** treatment with JAK inhibitors (e.g. baricitinib, upadacitinib) within 4 weeks or 5 half-lives (whichever is longer) prior to dosing on Day 1.
- 23. Other systemic treatments: mycophenolate mofetil, azathioprine, methotrexate, or calcineurin inhibitors within 4 weeks of Screening.

Prior / Concurrent Clinical Study Experience

- 24. **Blood / product loss**: participation in this study would result in loss of blood or blood products in excess of 500 mL within 3 months.
- 25. **Investigational drug:** use of any investigational drug within 30 days prior to the initial Screening visit, or 5 pharmacokinetic half-lives, or twice the duration of the biological effect (if known), whichever is longer.

Diagnostic assessments

- 26. **Hepatitis B**: patients will be excluded with **any** evidence of acute or chronic infection, or if interpretation of their results is unclear at the initial Screening visit. This includes:
 - a. Hepatitis B surface antigen (HbsAg) +
 - b. Anti-hepatitis B core (HBc) +

Note that, it is permissible to enrol patients who are anti-HBs+, *only* when this is attributable to vaccination and there is *no* history of previous infection.

Note that, if the serology test results remain unclear, a confirmatory hepatitis B (HB) deoxyribonucleic acid (DNA) + test may be performed.

- 27. **Hepatitis** C: patients will be excluded if there is *any* evidence of past or current hepatitis C infection at the initial Screening visit (hepatitis C antibody [quantitative immunoassay, qIA], hepatitis C radio immunoblot assay [RIBA or PCR]). NOTE: Participants with positive Hepatitis C antibody due to prior resolved disease may be enrolled, *only if* a confirmatory negative Hepatitis C RNA (PCR) test is obtained.
- 28. **HIV:** Positive human immunodeficiency virus (HIV) antibody test (obtained at the initial Screening visit) or known to have a historically positive HIV test.

Other Exclusions

29. **Alcohol:** Regular alcohol consumption within 6 months prior to the initial Screening visit defined as an average weekly intake of >14 units for males and >14 units for females.

One unit is equivalent to 8 g of alcohol: a half-pint (~240 mL) of beer, 1 glass (125 mL) of wine or 1 (25 mL) measure of spirits.

- 30. **Substance abuse:** Active substance abuse or a history of substance abuse (in the opinion of the Principal Investigator) within 6 months prior to the initial Screening visit. Note that *documented* medical use of marijuana or occasional recreational use of marijuana may be permitted subject to a priori agreement with the Medical Monitor.
- 31. **Compliance:** is unlikely to comply with scheduled study visits based on investigator judgment; has a history of a psychiatric disorder or condition that may compromise communication with the investigator.

5.3. Lifestyle Considerations

5.3.1. COVID-19 related restrictions

Participants will be required to adhere to the measures and procedures outlined locally at each of the investigative sites to reduce the risk of COVID-19 infections among trial participants and clinical site staff.

5.3.2. Meals and Dietary Restrictions

Not appropriate

5.3.3. Caffeine, Alcohol, and Tobacco

- There are no restrictions on ingesting caffeine- or xanthine-containing products (e.g., coffee, tea, cola drinks, and chocolate).
- Participants must abstain from alcohol for 24 hours before all scheduled visits.
- Participants who use tobacco products will be instructed that smoking will not be permitted while they are in the clinical unit.

5.3.4. Activity

Participants will abstain from strenuous exercise for 24 hours before each blood collection for clinical laboratory tests.

5.4. Screen Failures

Screen failures are defined as participants who consent to participate in the clinical study but are not subsequently randomized/entered in the study. A minimal set of screen failure information is required to ensure transparent reporting of screen failure participants to meet the Consolidated Standards of Reporting Trials (CONSORT) publishing requirements and to respond to queries from regulatory authorities. Minimal information includes demography, screen failure details, eligibility criteria, any protocol deviations and any serious adverse events (SAEs).

5.4.1. Re-screening

Participants who do not meet the eligibility criteria for this study may be rescreened once. Re-screened participants should be assigned a new participant number.

5.4.2. Re-testing of Clinical Laboratory Values during Screening

If a participant fails any of the laboratory criteria (e.g. variability around the threshold limit of a normal value, or spurious result), the test may be repeated once within the screening period. If the participant fails the laboratory criteria for a second time they will be considered a screen failure.

If a blood sample needs to be repeated due to sample handling problems, breakage or sample integrity, this is not considered a re-testing. Further details regarding the procedure for re-testing may be found in the SRM.

5.5. Criteria for Temporarily Delaying

Not applicable

6. STUDY INTERVENTION(S) AND CONCOMITANT THERAPY

Study intervention is defined as any investigational intervention(s), marketed product(s), placebo, or medical device(s) intended to be administered to a study participant according to the study protocol.

6.1. Study Intervention(s) Administered

| ARM Name | Active | Placebo | |
|---|---|---|--|
| Intervention Name | GSK1070806 Injection, 100 mg/mL | 0.9% sodium chloride injection | |
| Dosage Form | Solution for infusion | Solution for infusion | |
| Unit Dose Strength(s) | 100 mg/mL with 100 mg (1 mL) withdrawable per vial. | Variable volume | |
| Dosage Level(s) | 2 mg/kg - once (Groups 1 and 2) | The appropriate volume of 0.9% sodium chloride injection will be infused (IV) in the same manner as the corresponding active cohort | |
| Route of Administration | IV infusion (Groups 1 and 2) | IV infusion (Groups 1 and 2) | |
| Dosing Instructions | 1 hour IV infusion. Dilute into 100 mL sterile IV infusion bag 0.9% Sodium Chloride (for details, see Pharmacy Manual) | 1 hour IV infusion. | |
| Manufacturer/ Source of Procurement | Provided centrally by the Sponsor | Provided locally by the trial site | |
| Packaging and Labelling | Study Intervention will be provided in vials. Each vial will be labelled as required per country requirement. | N/A | |

6.2. Preparation/Handling/Storage/Accountability

For the required dose, the IP will be diluted in 0.9% sodium chloride injection and administered through IV infusion. Description of the methods and materials required for preparation and handling of GSK1070806 dosing solutions are detailed in the Pharmacy Manual.

Study treatment must be dispensed or administered according to procedures described herein and in the SRM and Pharmacy Manual.

The investigator or designee must confirm appropriate temperature conditions have been maintained during transit for all study intervention received and any discrepancies are reported and resolved before use of the study intervention.

Only participants enrolled in the study may receive study intervention and only authorized site staff may supply or administer study intervention. All study interventions must be stored in a secure, environmentally controlled, and monitored (manual or automated) area in accordance with the labeled storage conditions with access limited to the investigator and authorized site staff.

The investigator, institution, or the head of the medical institution (where applicable) is responsible for study intervention accountability, reconciliation, and record maintenance (i.e., receipt, reconciliation, and final disposition records)

Further guidance and information for the final disposition of unused study intervention are provided in the Study Reference Manual

Under normal conditions of handling and administration, study intervention is not expected to pose significant safety risks to site staff. Take adequate precautions to avoid direct eye or skin contact and the generation of aerosols or mists. In the case of unintentional occupational exposure notify the monitor, Medical Monitor and/or GSK study contact.

Precaution will be taken to avoid direct contact with the study intervention. A Material Safety Data Sheet (MSDS)/equivalent document describing occupational hazards and recommended handling precautions either will be provided to the investigator, where this is required by local laws, or is available upon request from GSK. In the case of unintentional occupational exposure notify the monitor, Medical Monitor and/or GSK study contact.

6.3. Measures to Minimize Bias: Randomization and Blinding

Blinded study with unblinded site pharmacist who is dispensing intervention

All participants will be centrally randomized using an Interactive Voice/Web Response System (IVRS/IWRS): RAMOS-NG.

Before the study is initiated, the telephone number and call-in directions for the IVRS and/or the log in information and directions for the IWRS will be provided to each site.

Participants will be randomized in a 2:1 ratio (Group 1 Biologic Naïve versus placebo) or 5:1 ratio (Group 2 Dupi-IR) to receive study intervention.

Investigators will remain blind to each participant's assigned study intervention.

In order to maintain the blind, an otherwise uninvolved 3rd party will be responsible for the dispensing of study intervention and will endeavour to ensure that there are no differences in the preparation time following randomization.

Unblinded monitors, and in the event of a Quality Assurance audit, the auditor(s) will be permitted access to un-blinded study intervention records at the site(s) to verify that randomization/dispensing has been done accurately.

A participant may continue in the study if that participant's intervention assignment is unblinded.

GSK's Global Clinical Safety and Pharmacovigilance (GCSP) staff may unblind the intervention assignment for any participant with an SAE. If the SAE requires that an expedited regulatory report be sent to one or more regulatory agencies, a copy of the report, identifying the participant's intervention assignment, may be sent to investigators in accordance with local regulations and/or GSK policy.

6.3.1. Controlled Early Access to Unblinded PK and PKPD Data

Designated independent representative(s) may be unblinded for performing population PK and PKPD dataset preparation and draft PK and PKPD model development at one or more time points throughout the trial using scrambled (random reassignment of subject identification numbers) PK and PKPD unblinded datasets.

TMF-14679521 **CONFIDENTIAL** 215253

6.4. Study Intervention Compliance

When participants are dosed at the site, they will receive study intervention directly from the investigator or designee, under medical supervision. The date and time of each dose administered in the clinic will be recorded in the source documents. The dose of study intervention and study participant identification will be confirmed at the time of dosing by a member of the study site staff other than the person administering the study intervention.

6.5. Dose Modification

Not applicable

6.6. Continued Access to Study Intervention after the End of the Study

Not applicable

6.7. Treatment of Overdose

For this study, any dose of GSK1070806 greater than 2 mg/kg will be considered an overdose.

GSK does not recommend specific treatment for an overdose.

In the event of an overdose, the investigator/treating physician should:

- Contact the Medical Monitor immediately to discuss details (actual dose administered) and next steps.
- Monitor the participant for any AE/SAE and clinical laboratory parameters for 24 weeks (until End of Study) following dosing.
- Document the quantity of the excess dose in the case report form (CRF).

6.8. Concomitant Therapy

The Medical Monitor should be contacted if there are any questions regarding prior, concomitant (including rescue) or non-permitted therapies.

Documenting therapies: Any medication or vaccine (including over-the-counter or prescription medicines, recreational drugs, vitamins, and/or herbal supplements) or other specific categories of interest (topical therapies for AtD) that the participant is receiving at the time of enrolment or receives during the study must be recorded along with:

- reason for use
- dates of administration including start and end dates
- dosage information including dose and frequency

6.8.1. Permitted Concomitant Therapies

Patients are to be instructed to apply topical non-medicated emollient at least once daily from Day -7 until at least Day 85.

The following concomitant therapies are permitted under the conditions described.

- Paracetamol/Acetaminophen, at doses of ≤ 2 grams/day at any time during the study.
- Oral anti-histamines (at the approved dose) at any time during the study.
- Intra-articular steroids (at the approved dose) at any time during the study.
- COVID-19 vaccines: see SRM for updated list of vaccines permitted per each country.
- Other concomitant medication may be considered on a case-by-case basis by the investigator (and in consultation with the Medical Monitor if required).

6.8.2. Prohibited Medications

Medications prohibited between Screening and Wk 12 are as follows owing to their potential to confound safety (and efficacy) assessments.

- Topical corticosteroids, topical calcineurin inhibitors, topical PDE4 inhibitors
- Oral immunosuppressants
- IV corticosteroids or biological immunosuppressants
- Phototherapy

If a participant requires a prohibited medication to address an urgent clinical need (e.g. extremely active disease, see Section 7.1.4) this should be recorded as a protocol deviation. The protocol deviation may affect the evaluability of the participant and should be discussed with the Medical Monitor in advance, if possible.

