7.1.4. Other Criteria

- Prohibited Medications: If the participant initiates *and continues* a prohibited medication (see Section 6.8.2) owing to a *considerable* worsening of AtD, s/he must be withdrawn from the study. Considerable worsening of AtD is defined as an increase in EASI of ≥25% from Baseline at 2 consecutive visits between Wks 4 and 12, according to the clinical judgement of the investigator.
- Surgery: the participant requires surgery prior to Wk 12.
- Pregnancy: the participant should be withdrawn from the study.

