1.1. Objectives, Estimands and Endpoints

Objectives	Endpoints
Primary	
To compare the clinical effect of a single intravenous (IV) infusion of 2 mg/kg of GSK1070806 versus placebo in moderate to severe Atopic Dermatitis in the Biologic Naïve (BN) population (Group 1).	Percent change from baseline (PCFB) in the Eczema Area and Severity Index (EASI) at Week 12
Secondary	
• To further compare the clinical effect (GSK1070806 versus placebo) in the BN population (Group 1).	 Change from Baseline (CFB) in the EASI at Week 12. EASI 50/75/90 defined as ≥ 50/75/90% reduction in the EASI from Baseline at Week 12. Investigator Global Assessment (IGA) score of 0 or 1 at Week 12.
To estimate the clinical effect of GSK1070806 in the dupilumab inadequate responder (Dupi-IR) population (Group 2).	PCFB in the EASI at Week 12.
To assess safety and tolerability (GSK1070806 versus placebo) in the combined AtD population (Groups 1 and 2).	 Incidence of serious adverse events (SAEs) and adverse events (AEs). Incidence of clinically important findings in: Vital signs Electrocardiogram Laboratory: haematology, clinical chemistry and urinalysis.
To assess anti-drug antibody (ADA) formation in the combined AtD population (Groups 1 and 2).	Incidence of ADAs

Primary estimand

The primary clinical question of interest is: What is the treatment effect on Eczema Area and Severity Index (EASI) after 12 weeks of treatment with a single intravenous (IV) infusion of 2 mg/kg GSK1070806 versus placebo in Biologic Naïve participants (Group 1) with moderate to severe Atopic Dermatitis in the absence of use of Rescue Therapy.

[figure not shown]
The primary estimand is described by the following attributes:

- Population: Biologic Naïve (BN) participants with moderate to severe Atopic Dermatitis.
- Treatment condition: A single 2 mg/kg one-hour IV infusion of either GSK1070806 or placebo at Day 1.
- o Variable / endpoint: Percent change from Baseline to Week 12 in the EASI.
- o Summary measure: Difference (GSK1070806 placebo) in mean percent change from baseline in EASI at Week 12.
- o Intercurrent events: Use of Rescue Therapy. It will be handled with a hypothetical strategy, i.e. values after use of Rescue Therapy will be set to missing.

Rescue Therapy is defined in this document as the use of any prohibited medication (as defined in the protocol section 6.8.2) that is considered as an important protocol deviation.

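### Rescue Therapy is tied to a route-limited list, so data after intramuscular or subcutaneous corticosteroids or injected methotrexate would stay in the analysis

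*Protocol*

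**What the plan says.** SAP 1.1 opens the definition with "Rescue Therapy is defined in this document as the use of any prohibited medication (as defined in the protocol section 6.8.2" and then adds a second condition: the use must count as an important protocol deviation. Both conditions are needed.

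Protocol 6.8.2 lists four things for the period from Screening to Week 12: topical corticosteroids, calcineurin inhibitors and PDE4 inhibitors; oral immunosuppressants; "IV corticosteroids or biological immunosuppressants"; and phototherapy.

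The entry criteria in protocol 5.2 are not limited by route. Exclusion 19, on systemic corticosteroids, reads "treatment within 30 days of dosing on Day 1. Note that, intra-articular steroids are permitted". Exclusion 23 covers "mycophenolate mofetil, azathioprine, methotrexate, or calcineurin inhibitors within 4 weeks of Screening". Both concern eligibility only, and the SAP definition does not refer to them.

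Every data rule is triggered by Rescue Therapy alone:
- Group 1 EASI is set to missing under MAR (SAP 4.2.2, and 4.3.1.2 for change from baseline).
- Group 1 binary responses are set to non-response (SAP 4.3.1.2).
- Group 2 EASI is set to missing under MAR (SAP 4.3.1.2).

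**The concern.** The rationale in SAP 1.1 is that the estimated effect should not be mixed with that of other treatments. As written, whether a systemic corticosteroid or methotrexate counts depends on how it was given. A flare treated with an intramuscular steroid leaves later EASI scores in the analysis as if the study drug or placebo had produced them.

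The direction depends on who uses it. Use on placebo dilutes the Group 1 difference, and use on active inflates it. Group 2 is analysed without a comparator, so any gain is credited to GSK1070806. A binary endpoint changes only if the drug turns that participant into a Week 12 responder.

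**Working it through.** **Reading the text.** An intramuscular or subcutaneous corticosteroid is not topical, oral, intravenous or biological. Injected methotrexate is neither oral nor biological. Neither is on the 6.8.2 list, so neither can be Rescue Therapy, even if the use is judged an important deviation.

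**Could another provision close the gap?**
- Protocol 6.8.1: of injected steroids, only intra-articular is expressly permitted. For the rest, "Other concomitant medication may be considered on a case-by-case basis by the investigator". That allows a decision about the drug but does not make it prohibited.
- Protocol 7.1.4: a participant who starts and continues a prohibited medication for considerable "worsening of AtD, s/he must be withdrawn from the study". This refers to the same 6.8.2 list.
- SAP 6.1.3: the review before unblinding decides importance, not whether a drug is listed.
- SAP 4.2.4: the treatment-policy estimand keeps the same data, so comparing the two estimands would not reveal the use.

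**Reproducing the plan's figures.** Inputs from protocol 9.2:
- n = 20 active and 10 placebo; SD 50; true placebo PCFB -30.
- Placebo prior 0.285 N(-31.56, 5.67) + 0.215 N(-31.21, 11) + 0.5 N(-30, 50).
- Active prior N(-30, 50).

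With SD known, each placebo component k has posterior variance 1/(1/s_k² + n/2500), and its weight is updated in proportion to w_k × N(ȳ; m_k, s_k² + 2500/n). The active posterior variance is 1/(1/2500 + 20/2500) = 119.05. The criterion is met when Σ W_k Φ((-15 - (a - p_k))/√(V_a + V_k)) > 0.75, where a and p_k are the posterior means. Integrating over the sampling distributions of the two arm means gives:
- -15% row: 82.6 / 43.9 / 18.4 / 2.5%, as printed.
- -7.5% row: 92.8 / 66.6 / 37.7 / 7.8%, as printed.

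**One user retained, gaining an assumed 20 or 50 points.** The placebo mean becomes -30 - 20/10 = -32, or -30 - 50/10 = -35. At a true difference of -25% the active mean becomes -55 - 20/20 = -56, or -55 - 50/20 = -57.5.

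| -15% criterion | No user | Placebo user, 20 / 50 | Active user, 20 / 50 |
|---|---|---|---|
| True -25% | 43.9% | 41.2% / 37.2% | 46.9% / 51.3% |
| True 0 | 2.5% | 2.1% / 1.5% | 2.9% / 3.7% |

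Wider range, also assumed: with 1 to 3 of 10 placebo participants each gaining 30 to 60 points, the placebo mean moves by -3 to -18. At a true -40%, the 82.6% then falls to between 79.4% and 56.7%.

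**Group 2** (true -30%, -37.5% criterion). SE = 50/√15 = 12.91. With no user, Φ((-37.5 + 30)/12.91) = 28.1%, as printed. One user gaining 20 points: Φ((-37.5 + 31.33)/12.91) = 31.6%. Gaining 50 points: Φ((-37.5 + 33.33)/12.91) = 37.3%.

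**Binary endpoints.** One changed outcome is 1/10 = 10 points of observed rate on placebo, or 1/20 = 5 points on active.

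**The same user deleted instead** (true -25%). If the user is average, n falls to 9 or 19 and the figure is 43.4% in either case. If the untreated PCFB would have been 0, the remaining means are -300/9 = -33.33 (placebo) and -1100/19 = -57.89 (active). Under MAR, suppose Week 8 shows the same deviation and has correlation ρ with Week 12 (assumed; the documents give none). The mean is then -33.33 + 3.33ρ or -57.89 + 2.89ρ, with effective n = (n - 1) + ρ².

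| ρ | Placebo user deleted | Active user deleted |
|---|---|---|
| 0 | 39.1% | 51.8% |
| 0.5 | 41.4% | 47.7% |
| 0.7 | 42.3% | 46.2% |

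Group 2, same user: Φ((-37.5 + 32.14)/13.36) = 34.4% at ρ = 0, and 30.1% at ρ = 0.7.

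**The case against.** The strongest case for leaving the text alone has three parts.

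**No harm is shown.** The documents give no frequency for such use, the trial tests no formal hypothesis, and its sample size supports only a preliminary assessment. This stands: the impact may be nil.

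**Deletion is not always closer to the planned figure.** For a poor responder with a 20-point gain and no recovery from earlier visits, deletion gives 39.1% against 41.2% retained on placebo, and 51.8% against 46.9% on active. In Group 2 it gives 34.4% against 31.6%. This also stands. It rules out arguing for the change on the ground of a smaller shift. It does not justify a data rule that contradicts the stated estimand.

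**Other controls make silent use unlikely.** Inclusion 9 asks for stable concomitant regimens. Section 6.8 says "The Medical Monitor should be contacted if there are any questions regarding prior, concomitant (including rescue) or non-permitted therapies". The investigator may withdraw a participant under 7.2. SAP 6.1.4 summarises all concomitant medication by ingredient, so such use would be visible at reporting. These controls are real, but none changes the SAP 1.1 definition or the analysis dataset.

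A smaller objection is that 6.8 does not name route among the items to record. The present list already separates topical, oral and intravenous use, so it cannot be applied without knowing the route either.

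**Conclusion.** The concern holds on the wording. Followed exactly, the plan would keep data after an unlisted systemic agent and report them within an estimand defined to exclude other treatments. It may be a drafting slip, since 6.8.2 states the same aim of avoiding confounding and the entry criteria are not limited by route.

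The consequence is small but real if the event occurs. One retained Group 1 user moves the 43.9% figure by roughly 3 to 7 points in either direction, and one Group 2 user raises 28.1% by about 3.5 to 9 points. These sizes rest on one user, an assumed gain of 20 or 50 points, and the plan's SD of 50. They show scale and do not predict what will happen.

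**What to change.** Amend protocol 6.8.2 to prohibit, between Screening and Week 12, systemic corticosteroids by any route except intra-articular, and systemic immunosuppressants by any route, alongside the existing topical, biological and phototherapy entries. SAP 1.1 then works unchanged. This wording also settles whether an oral corticosteroid counts as an oral immunosuppressant.

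If only the SAP is changed, define Rescue Therapy by these classes regardless of route. Apply one importance test to listed and added agents alike, judged blind before unblinding from the reason, dates and dose, so that a minor or unrelated use is treated the same by any route. Keep the planned handling: missing under MAR for continuous endpoints and non-response for binary ones.

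The cost is one protocol line, or SAP wording plus a blinded look at the medication record. Section 6.8 already requires that any medication "that the participant is receiving at the time of enrolment or receives during the study must be recorded along with" its reason, dates and dose. The downside is a few more values missing under MAR. Per participant, that is about half a point on the 43.9% figure if the user is average (43.4%), and several points if the user is a poor responder and earlier visits recover nothing (39.1% or 51.8%).
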